9.4 Reporting AEs and USADEs

All SAEs and USADEs will be documented as outlined above and reported in writing to the Sponsor within 72 hours of knowledge of the event. The Adverse Event Case Report Form [REDACTED]

[REDACTED] will also be submitted to the study Sponsor within 72 hours of knowledge of the event.

If the event resulted in the death of a subject, the event will be reported to the Sponsor within 24 hours of knowledge of the event.

The Sponsor Medical Monitor is the contact for SAEs and/or USADEs at the following E-mail: [REDACTED].

Additional follow-up information may be requested by the Sponsor. In addition, safety information may be shared with regulatory agencies and other participating sites, as required by applicable law and regulation. AEs and SAEs will be reported to the EC/IRB per their policy.

Study Title: Development Of Medical Ultrasound Systems, Accessories, And

Components - GE Bangalore

Study Number: 110.08-2015-GES-0004

9.5 Device Deficiencies/Complaints Definitions and Reporting

Device deficiency: an inadequacy of a medical device with respect to its identity, quality, durability, reliability, safety, or performance, such as malfunctions, use errors, and inadequate labelling [ISO 14155:2011 3.15].

This study is intended as an iterative feasibility and optimization study, in which it is expected that devices may perform atypically in ways that do not pose safety issues during the course of optimization. Expected atypical function as a routine part of engineering investigation that does not pose a safety risk is not considered a device deficiency.

Device Complaints: Device complaints will be considered reports of unexpected atypical device function and device issues that are suspected by study staff to pose a safety risk. Device complaints will not include expected atypical function occurring as a routine part of engineering investigation, so long as such atypical function is not expected to pose a safety risk.

Study staff and/or authorized representatives of the Sponsor at the site should report complaints/deficiencies to the Clinical Affairs Project Manager, including:

- a brief description of the issue,
- date and time of occurrence,
- subject ID numbers of affected subject(s), and
- safety issue (Y/N)

The Principal Investigator is responsible for notifying the Sponsor within 72 hours in the event that there is any device issue that could potentially lead to a SAE.

9.6 Managing the Subject Transition from Scanning Area to Hospital

For cases that require hospitalization, there is an agreement with a hospital located close to the facility.

An ambulance will be available for the duration of scanning activity at the GEHC on-site medical center for emergencies. The medical center shall contact the medical service provider at the given emergency contact number in the hospital to inform them of any medical emergency at the facility.

The medical care of the participating subject will be provided at the Hospital noted in [Appendix A: Study Contacts](#). The PI will be in contact with attending physician until the complete resolution of the issue and until the reporting requirements are met.

10. ETHICAL CONDUCT OF THE STUDY

The study will be carried out in accordance with the protocol and with principles enunciated in the current version of the Declaration of Helsinki; the guidelines of Good Clinical Practice (GCP) for medical devices, as set forth by ISO 14155:2011 and ISO 14971:2012; and applicable requirements of the India Ministry of Health and Family Welfare (MOHFW).

The study will be conducted and reported in accordance with applicable policies of the ethics committee (EC) and governing regulatory authorities.

Study Title: Development Of Medical Ultrasound Systems, Accessories, And

Components - GE Bangalore

Study Number: 110.08-2015-GES-0004

If national or regional EC requirements are less strict than the requirements of GCP, such as ISO 14155:2011 for medical devices, the Sponsor shall apply the principles of this International Standard to the greatest extent possible, irrespective of any lesser requirements, and shall record such efforts.

10.1 Ethics Committee

The responsible Principal Investigator at each site will ensure that approval from an appropriately constituted EC is attained for the clinical study prior to enrolling subjects, and the Principal Investigator will ensure that documentation of approval is maintained for the duration of the study.

The Principal Investigator will ensure that the Sponsor is notified of any withdrawal of EC approval within 5 working days of such occurrence. If approval is terminated or suspended, the Principal Investigator will promptly notify the Sponsor and provide written explanation.

Copies of all EC submissions, approval letters, Informed Consent Forms (ICF), and other correspondence shall be sent to the Sponsor, and originals shall be maintained in the Site Regulatory Binder.

10.2 Regulatory Agency Approval Requirements

Indian clinical trial requirements regarding a governmental licensing authority permission to conduct a clinical trial (in Drug and Cosmetics Rules, 1945 – Rule 122 DAC) are deemed not applicable to trials on low to medium risk devices not required to be registered for commercialization in India. Ethics committee approval is required prior to clinical trial initiation.

10.3 Management of Protocol Modifications and Amendments

Substantial amendments will only be implemented after approval of the EC, in accordance with their policy.

A deviation is any instance(s) of failure to follow, intentionally or unintentionally, the requirements of the protocol. Under emergency circumstances, deviations from the protocol to protect the rights, safety, and wellbeing of human subjects may proceed without prior approval of the Sponsor and, if applicable, the EC or competent authority (CA). Such deviations shall be documented and reported to the Sponsor and the IRB as soon as possible. Deviations will be reported as:

- **Critical Deviations:** Deviations that significantly affect the safety, efficacy, integrity, or conduct of the study. These deviations must be reported to the Sponsor no later than 5 working days from awareness of occurrence and reported to the EC per the deviation reporting policy.
- **Non-Critical Deviations:** Protocol deviations that do not significantly affect the safety, efficacy, integrity, or conduct of the trial. These deviations must be documented on the CRF Protocol Deviation page and will be reviewed by the study monitor.

Non-substantial modifications may be made during the normal course of device optimization, maintenance, and feasibility testing. Non-substantial modifications will be communicated per applicable laws, local site procedures, and to the EC per their policy.

10.4 Participant Information and Informed Consent

Written informed consent will be obtained from all subjects prior to participating in the study, per the determination of the IRB/EC. Signed copies of the informed consent form will be stored by the site. Trained Study

Study Title: Development Of Medical Ultrasound Systems, Accessories, And

Components - GE Bangalore

Study Number: 110.08-2015-GES-0004

Staff will conduct the informed consent process per regulatory guidelines, which include: the subject will be allowed ample time to review the ICF and have all questions answered to their satisfaction; the subject may take the ICF home to review with family members or others prior to agreeing to participate in the study; upon agreeing to participate in the study, the subject will sign and date the informed consent; the person who obtained consent from the subject will also sign and date the document.

The subject will be given a copy of the signed informed consent form and the original will be retained with the study record.

Per the recommendation of the American Institution of Ultrasound in Medicine (AIUM) recommendation (2007), subjects having ultrasound scans for the purposes of training or research will be informed via the informed consent form that the anticipated exposure and conditions are not expected to expose the subject to greater risks compared with routine diagnostic ultrasound procedures commonly performed in clinical practice.²⁵

If a study scan is performed on a subject without obtaining informed consent, this will be considered a critical deviation and reported to the Sponsor and the IRB/EC within 5 working days of the occurrence.

Study documents that contain personally identifiable private information will be maintained securely at the site. Study records will only be made accessible to third parties (such regulatory agencies) as necessary for the conduct of the study and as required by law. Authorized representatives of the Sponsor, including Study Monitor(s) and Quality Auditor(s), may review the study records as necessary to ensure the quality and conduct of the study. All reasonable efforts will be made to protect the confidentiality of each subject's personally identifiable private information obtained during the course of this study.

10.4.1 Additional Informed Consent and Privacy Requirements

Wipro GE Healthcare (WGE) is registered with Appropriate Authority, Bengaluru Urban District ("Appropriate Authority") in compliance with the Pre-conception and Pre-diagnostics Techniques (Prohibition of Sex Selection) Act, 1994 and Rules therein ("PNDT Act") and is required to provide monthly reports of all scans done to the Appropriate Authority in accordance with the PNDT Act.

Information collected and reported to the Appropriate Authority include but is not limited to each volunteer subjects name, age, sex/gender, father/husband's name, address, type and date of ultrasound scan, scan facility and scan operator's name.

An additional 'PNDT Consent Form' will be obtained from all volunteer scanning subjects prior to participation in the study.

10.5 Early Termination/Suspension of the Study

The Sponsor may terminate the study prematurely according to certain circumstances. Examples of such circumstances include ethical concerns, insufficient participant recruitment, participant safety concerns, alterations in accepted clinical practice that make the continuation of a clinical trial unwise, early evidence of benefit or harm of the research product, or for any other reason.

The Sponsor will promptly notify the investigators of any determination to terminate the study outside of the protocol timeframe. The Sponsor will provide each investigator with written guidelines/instructions on termination processes and timelines.

The site is responsible for reporting the early termination to the responsible EC/IRB, per their policy.

Study Title: Development Of Medical Ultrasound Systems, Accessories, And

Components - GE Bangalore

Study Number: 110.08-2015-GES-0004

11.QUALITY ASSURANCE AND CONTROL

11.1 Data Management

Data management processes for handling study data will be maintained by the Sponsor.

11.1.1 Completion of Case Report Forms (CRFs)

The data reported on the CRFs may serve in full or part as the source documents for the study, when no other source documents exist. Paper CRFs and/or electronic CRFs (eCRFs) will be used to collect data. The Sponsor will provide CRFs and train study staff on completion of CRFs using Good Documentation Practices (GDP). CRF Completion Guidelines (CCG) may be provided by the Sponsor to help facilitate training.

CRFs are to be completed as information becomes available at the site. CRFs should be signed by indicated parties, in indicated area(s), to certify the contents of the form. The Principal Investigator is ultimately responsible for ensuring completion of CRFs.

If discrepancies are discovered on paper CRFs during monitoring, whether during monitoring or during data review by the study team, the site will make necessary corrections directly to the CRF(s). The Sponsor may request to review CRF data, at its discretion. The Sponsor may provide a Data Clarification Form (DCF) to the site to correct or clarify discrepancies.

11.1.2 Data Handling and Record Keeping

All documents and data shall be produced and maintained in a manner that assures control and traceability.

11.1.3 Source Data and Documents

Source data includes information in original records, certified copies of original records of clinical findings, observations, or other activities for the study. Source documents for each subject must be retained throughout the investigation, including printed or electronic documents containing source data. Elements should include:

- **Source data and documentation** relevant to data recorded for subject screening and CRF corroboration (CRFs may serve as source documentation)
- **Subject records** containing the completed ICFs and CRFs
- **Regulatory binder** containing the protocol and any subsequent amendments, IRB submissions and approvals, blank ICF(s), recruitment materials, correspondence, and site logs

The Principal Investigator or institution shall provide direct access to source data during and after the clinical investigation for monitoring, audits, IRB review, and regulatory authority inspections.

11.1.4 Archiving

All study documents will be retained securely at the site with limited access.

Study records will be retained for a period no less than the period required by applicable laws and regulations, at present a minimum of 10 years per CFDA Order No. 25. Archived study records will be made available for inspection by authorized representatives of the Sponsor or to third parties, such as regulatory agencies, as required by local law. No study records will be destroyed without prior Sponsor notification and approval.

Study Title: Development Of Medical Ultrasound Systems, Accessories, And

Components - GE Bangalore

Study Number: 110.08-2015-GES-0004

12. MONITORING PLAN

In collaboration with the site, the Sponsor will ensure proper monitoring of the study to confirm that all the research requirements are met. Monitoring visits will oversee the progress of a clinical investigation and ensure that it is conducted, recorded, and reported in accordance with the protocol, written procedures, Good Clinical Practice (GCP) ISO 14155:2011, and the applicable regulatory requirements.

12.1 Confidentiality and Data Protection

The investigator affirms and upholds the principle of the participant's right to privacy, and the investigator shall comply with applicable privacy laws. Anonymity of the participants shall be guaranteed when presenting the data at scientific meetings or publishing data in scientific journals.

Individual subject information obtained as a result of this study that contains information that identifies a subject will be considered confidential, and disclosure to third parties will be prohibited unless specific consent from the subject has been obtained.

Third parties, as authorized by the Sponsor, may be present during study procedures and have incidental access to subject information. To the extent possible, the study staff will ensure that risks to the subject's confidentiality are minimized.

Individual subject information obtained as a result of this study will be considered confidential, and disclosure to third parties will be prohibited. Subject confidentiality will be further ensured by utilizing subject identification code numbers. For data verification purposes, authorized representatives of the Sponsor, a competent authority (CA), or an Institutional Review Board (IRB) or Ethics Committee (EC) may require direct access to parts of the subject records and any other information, such as payment or financial information, collected during the course of the study, in accordance with applicable laws and regulations.

12.1.1 Storage and Use of Data and Images

Ultrasound images and associated data will be collected and disclosed to the Sponsor as part of this study. De-identified data, which has had personal identifying information removed, may be stored and used by the Sponsor indefinitely. The Sponsor and/or its authorized representatives may use and disclose to third parties any de-identified data for future technology and engineering development, marketing purposes, education, regulatory submissions, publications, or any other possible uses identified by the Sponsor.

12.1.2 Subject De-Identification

Subjects will be assigned a unique Subject Identification Number and study data, including electronic image files, provided to the study Sponsor or others at GE Healthcare not directly participating in the conduct of the study will not contain any personally identifiable information about subjects.

12.2 Publication Policy

No cohort-based results from this study are planned for publication. De-identified data, including images, may be stored and used indefinitely by GE Healthcare for unspecified future purposes, including but not limited to, future analysis for technology development, marketing materials, product brochures, training and educational materials, scientific presentations, and other public purposes.

Study Title: Development Of Medical Ultrasound Systems, Accessories, And

Components - GE Bangalore

Study Number: 110.08-2015-GES-0004

13.ADDITIONAL STUDY MATERIALS/REFERENCES

APPENDIX B: SAFETY GUIDELINE TRAINING MATERIALS

Figure B.1 – Non-Obstetrical Scanning²⁰

Application	Values to monitor (A)	Thermal Index value		Mechanical Index value	
		0 – 1.0	> 1.0	0 - 0.3	> 0.7
General abdominal	Usually TIB and MI.	✓	(B) restrict time to 1.0<TIB≤1.5 : 120 min 1.5<TIB≤2.0 : 60 min 2.0<TIB≤2.5 : 15 min 2.5<TIB≤3.0 : 4 min 3.0<TIB≤4.0 : 1 min 4.0<TIB≤5.0 : 15 sec 5.0<TIB≤6.0 : 5 sec TIB>6: not recommended	✓	(C) risk of cavitation with contrast agents
Peripheral vascular	[use TIC and MI if bone closer than 1 cm; TIS and MI only if bone does not come into the image]				
Unlisted applications					
Eye	TIS and MI recommended	✓	Scanning of the eye is not recommended	✓	(C) risk of cavitation with contrast agents
Adult transcranial (imaging and stand-alone) (D)	TIC and MI	✓	(B) restrict time to 0.7<TIC≤1.0 : 60 min 1.0<TIC≤1.5 : 30 min 1.5<TIC≤2.0 : 15 min 2.0<TIC≤2.5 : 4 min 2.5<TIC≤3.0 : 1 min TIC>3: not recommended	✓	(C) risk of cavitation with contrast agents
Peripheral pulse monitoring	TI or MI are not usually available for dedicated peripheral pulse monitors.	The output from CW Doppler devices intended for monitoring peripheral pulses is sufficiently low that their use is not contra-indicated, on safety grounds			

✓: There is no known reason to restrict scanning times in this region.
 A: Many scanners allow MI and one of the TI values to be displayed simultaneously: the most appropriate TI value depends on the clinical application.
 B: TI > 1.0 - the overall exposure time (including pauses) should be restricted.
 C: MI > 0.7 - there is a risk of cavitation if an ultrasound contrast agent containing gas micro-spheres is being used. There is a theoretical risk of cavitation without the presence of ultrasound contrast agents. The risk increases with MI values above this threshold.
 D: Transcranial ultrasound investigations may require higher acoustic output or longer monitoring times than other applications. When times longer than those recommended here are required, it is recommended that monitoring is paused regularly to minimise exposure.

For ophthalmic applications, the maximum attainable value for the Thermal Index should be less than or equal to 1, the maximum attainable value of the Mechanical Index should be less than or equal to 0.23 and the maximum attainable value of the derated spatial peak time average intensity, $I_{spta,3}$ should be less than or equal to 50 mW/cm².

End of Document

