1.3 Device Risk and Benefit Analysis

Diagnostic ultrasound devices, components, and accessories are generally considered non-significant risk devices that safely and effectively use reflection of sound waves from different tissues in the human body to generate images. Ultrasound devices have a consistent safety and bioeffect profile that has been studied and reported.^{16, 17} Diagnostic ultrasound devices have been used since the 1950s and are considered one of the safest imaging modalities available. No confirmed adverse biological effects on humans have been reported, though it is possible that the short-term and long-term biological effects of ultrasound are not completely known.^{13, 18}

The possibility of adverse health effects from the sound waves produced by diagnostic ultrasound systems is remote. Ultrasound imaging devices used in this study typically adhere to the exposure limits set forth in the *WFUMB Recommendations on Non-medical Use of Ultrasound* (2013)¹⁹ and the *British Medical Society Guidelines for the Safe Use of Diagnostic Ultrasound Equipment* (2009), as detailed in the safety appendix.²⁰ These standards are employed extensively in other ultrasound studies conducted by the Sponsor. Factors involved in the dose of energy delivered to tissue include the ultrasonic power level and volume of tissue exposed. Prudent and widely accepted limitations are employed in this study to the exposure time and power level during use (as detailed in [Appendix B: SAFETY GUIDELINE TRAINING MATERIALS](#)).

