6.1.3 Activities during a Study Scan

Each subject may elect to participate in up to five (5) study scans per day lasting up to 60 cumulative minutes each with approximately a 15 minute break before starting another study scan. Ophthalmic scanning will be limited to no more than 15 cumulative minutes of scan time per eye, per day.

The start time of a study scan begins when the device contacts the subject's skin and scanning begins; the stop time is when the study scan is complete. Pauses in active scanning are not counted towards the cumulative scan duration.

The study ultrasound scan will be performed while the subject is lying, sitting, or standing. Subjects may be asked to shift positions, to hold still, complete breath hold(s), bear down (Valsalva maneuver), or other maneuvers necessary for the scanning procedure. In some cases, device accessories (e.g. coupling agents, probe, land marking, tracking, monitoring, or other ultrasound device components) may be placed in direct contact with the subject's skin and/or superficial marks may be placed with a semi-permanent medical grade marker.

Scanning may be performed for target anatomic areas using a variety of non-invasive, transcutaneous techniques, such as scanning abdominal, musculoskeletal, breast(s), peripleural, transcranial, ophthalmic, cervical/neck, cardiac, vascular, extremity, soft tissue, and other accessible anatomical regions. More than one region may be scanned in a single study scan.

Study Title: Development Of Medical Ultrasound Systems, Accessories, And Components - GE Bangalore

Study Number: 110.08-2015-GES-0004

If a subject reports discomfort or wishes to stop the scan for any reason, the Study Staff will respond to subject's concerns and adjust the scanning procedures or, if the concern is not able to be resolved, discontinue the study scan. There will be no negative repercussions to the subject for reporting discomfort or deciding to stop the study scan, and he/she may still participate in future visits. Non-medical care will be provided to the subject to alleviate any discomfort, as needed.

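### For transcranial scans at TIC 0.7 to 1.0, Figure B.1 can be read as a 60-minute limit or as no limit, and its clock includes pauses that section 6.1.3 leaves out

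*Protocol*

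**What the plan says.** Section 1.3 of the protocol says of the exposure controls: "Prudent and widely accepted limitations are employed in this study to the exposure time and power level during use", and refers to Appendix B for the detail. Section 6.1.3 puts transcranial scanning in scope ("such as scanning abdominal, musculoskeletal, breast(s), peripleural, transcranial, ophthalmic, cervical/neck") and allows "up to five (5) study scans per day lasting up to 60 cumulative minutes each", with a break of roughly 15 minutes between scans. Time during which active scanning is paused does not count towards that duration. Section 6.1.3 gives no transcranial limit that depends on the thermal index.

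Figure B.1 in Appendix B has two thermal index columns, one for 0 to 1.0 and one for values above 1.0. For adult transcranial scanning:

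- The index to watch is TIC, together with MI.
- The 0 to 1.0 column is ticked. The legend explains the tick as "There is no known reason to restrict scanning times in this region".
- The column for values above 1.0 cites note B and then lists time limits, of which the first is "0.7<TIC≤1.0 : 60 min".
- Note B reads "TI > 1.0 - the overall exposure time (including pauses) should be restricted".
- Note D says that transcranial work may need longer times than those listed and recommends regular pauses when it does.

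**The concern.** Between TIC 0.7 and 1.0 the row appears to give two answers: a 60-minute limit and a tick that stands for no reason to limit time. Note B, to which the row's own cell refers, starts above that range.

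Appendix B is titled as training material and is the only place where an operator can find an index-dependent transcranial limit. Two operators could both follow the sheet in good faith and allow different exposures. Section 10.3 defines a deviation as a failure to follow the protocol's requirements, and a limit with two readings cannot be audited consistently. The appendix and section 6.1.3 also measure time by different rules, so even an agreed number of minutes would not mean the same thing in both places.

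**Working it through.** The protocol states no derived figure to reproduce here. The check compares the stated intervals and then does simple arithmetic on the ceilings.

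**1. Threshold, transcranial row (Appendix B)**

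| Element | TIC range covered | What it says about time |
|---|---|---|
| Tick under the first column | 0 to 1.0 | no known reason to restrict |
| First listed limit | above 0.7, up to 1.0 | 60 min |
| Heading of the column holding that limit | above 1.0 | restricted |
| Note B | above 1.0 | restrict, pauses included |

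Overlap of the ticked and the limited range: [0, 1.0] ∩ (0.7, 1.0] = (0.7, 1.0]. Over that interval the row carries both statements. Note B and the column heading do not reach it.

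**2. Comparison row**

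The general abdominal row starts its limits at TIB above 1.0. Heading, tick and note B agree there, with no overlap. Of the rows with listed time limits, only the transcranial one breaks the pattern.

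**3. Size of the difference in permitted time, TIC 0.7 to 1.0**

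If the tick governs, the remaining ceiling is that of section 6.1.3: 5 scans × 60 min = 300 cumulative minutes per day. If the listed limit governs, the answer depends on its unit, which the table does not give.

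- Unit is per day: 300 min against 60 min, and 300 / 60 = 5. This is an upper bound. It needs five full-length transcranial scans of one subject in one day, all in this TIC range.
- Unit is per scan: 60 min against 60 min, a ratio of 1. Only the way of counting then differs.

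**4. Counting of time**

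Let *a* be active scanning minutes and *p* minutes of pause within one scan. Section 6.1.3 counts *a*. Note B counts *a* + *p*. A scan with *a* = 60 and any *p* > 0 is within the section 6.1.3 ceiling but has an overall time of 60 + *p* > 60 under note B. Section 6.1.4 has staff record a duration of scan exposure for each scan and does not say which of the two counts it is. This mismatch touches every row that cites note B, not only the transcranial one.

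**The case against.** Several parts of the opposing case stand.

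- **Note B does not say that time is free below 1.0.** It says restriction is needed above 1.0. A row-specific limit from 0.7 is stricter than a general note and can coexist with it. The direct conflict is therefore between the limit and the row's own tick and column. Note B adds to the ambiguity because the cell cites it, but it would not prove a contradiction alone.
- **Table layout.** The table has merged cells, and its grid is not preserved in the text of the protocol. A heading specific to the transcranial row may have been lost, so heading and tick must be checked in the issued layout.
- **Note D makes the table guidance rather than a hard ceiling.** True, but it speaks of exceeding the listed times and so still needs one listed time.

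Three stronger readings might be inferred, and the documents do not support them.

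- **That the eye row contradicts itself.** It is ticked for MI 0 to 0.3, while the closing paragraph says "the maximum attainable value of the Mechanical Index should be less than or equal to 0.23". The tick concerns scanning time under a heading shared by all rows, and the 0.23 figure caps attainable output. A device held to 0.23 lies inside the ticked band, so both can be met. The ophthalmic thermal cap ("the maximum attainable value for the Thermal Index should be less than or equal to 1") agrees with the eye row. Eye scan time is also limited separately in section 6.1.3. At most, a cross-reference is missing.
- **That exposure differs five-fold.** This holds only if the 60 minutes is a daily limit, which the table does not state.
- **That the minimal-risk statement loses its basis.** Section 1.3.1 ties that statement to the FDA, AIUM/NEMA and IEC limits, with monitoring of output and dwell time, and not to the Appendix B thresholds.

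**Conclusion.** The transcranial inconsistency stands on the text as it reads. For TIC above 0.7 and up to 1.0, Figure B.1 supports both a 60-minute limit and no table limit. The size runs from no difference in nominal minutes (limit per scan) to at most 300 against 60 minutes per day (limit per day). The conflict over pauses stands under either unit and does not depend on the table layout, since note B and section 6.1.3 are both running text.

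The threshold part assumes that the tick and the column heading apply to the transcranial row as they appear.

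The point should be corrected because it bears on subject protection, concerns a scan type in scope and is cheap to mend. It does not touch the primary endpoint, which in section 3.3.1 is a count of scans by type. No view is taken here on which threshold or which count is right.

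**What to change.** 1. Check the transcranial row's heading and tick against the issued layout of Figure B.1.
2. Reconcile the row's first limit, the column boundary, the tick and note B, so that one threshold applies to transcranial scanning. State whether the listed minutes are per scan or per day.
3. Reconcile note B with the counting rule in section 6.1.3, so that pauses are treated in one way, and say in section 6.1.4 which duration is recorded.
4. Cross-reference the reconciled limit in section 6.1.3. Optionally, add a pointer from the eye row to the ophthalmic maximum in the closing paragraph.

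The sponsor decides which threshold, unit and counting rule to keep. The cost is a correction to one appendix table, a sentence or two in sections 6.1.3 and 6.1.4, and retraining of operators on the revised sheet. Ethics committee handling follows section 10.3.
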